The SPC (included in the Lojuxta® SPC in lieu of an Investigator's Brochure [IB]; see Section 18.1 *Source Documents*) provides guidance in key areas to minimise risk to patients during treatment with lomitapide, which is reflected in the design of this study. Use of lomitapide in patients with moderate or severe hepatic impairment, active liver disease, or pregnancy is contraindicated (see Section 5.2 *Exclusion Criteria*). Contraindications also include co-administration with strong or moderate inhibitors of CYP 3A4 and co-administration with doses of simvastatin >40 mg (see Section 7.6.3 *Non-Permitted Concomitant Medication, Food or Substances*). In the presence of atorvastatin (a weak CYP 3A4 inhibitor), lomitapide should be taken 12 hours apart. Since patients will be required to remain on their concomitant LLT (including LA when applicable) established during the 6-week Run-in Period during the Efficacy Phase of the study through Week 24±3 days, a potential concomitant treatment with atorvastatin will remain unchanged during the Efficacy Phase, when lomitapide dosing will start. If atorvastatin is given concomitantly, it should be administered in the morning to separate it from lomitapide dosing by 12 hours. If during the 80-week Safety Phase it is not possible to administer atorvastatin and lomitapide 12 hours apart, the lomitapide dose should be reduced by half. After a minimum period of 4 weeks following dose reduction the patient can be re-challenged with a higher dose of lomitapide once these issues resolve (i.e., if atorvastatin can be administered 12 hours apart or if atorvastatin is discontinued), but the dose during the Safety Phase cannot exceed the MTD established during the Efficacy Phase unless eligibility for exceptional dose escalation is met (described in Section 7.3.1 *Dose Escalation, Dose*

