*Reduction and Re-challenge*). For patients on a stable maintenance dose of lomitapide who receive any other weak CYP 3A4 inhibitor, the dose of the medications should be separated by 12 hours (see Section 7.3.3 *Dose Modification for Concomitant Medication*). Use in patients with known significant or chronic bowel disease is also contraindicated since MTP inhibition is known to cause fat malabsorption and steatorrhea. Use in patients with rare hereditary problems of galactose intolerance, the Lapp-lactase deficiency or glucose-galactose malabsorption, are contraindicated in accordance with EU guidance (EC Volume 3B Guidelines, *Medicinal Products for Human Use, Safety, Environment and Information: Excipients in the Label and Package Leaflet of Medicinal Products for Human Use*, July 2003) since the drug product contains lactose (see Section 5.2 *Exclusion Criteria*). Hepatic aminotransferase levels must be determined prior to initiating therapy, and then monitored prior to each dose escalation, and regularly during treatment (see Section 1.2 *Flow Chart of Study and Follow-up*). In the event that hepatic aminotransferases become elevated, a detailed algorithm for dose adjustment or treatment discontinuation is provided (see Section 7.3.2 *Dose Modification, Interruption or Discontinuation for Adverse Events*). This algorithm is based on the approach agreed with the DSMB hepatologist that was used successfully in the pivotal phase III study and is consistent with the FDA's draft guidance *Drug-Induced Liver Injury: Premarketing Clinical Evaluation*, October 2007. Dietary advice, including fat content (see Section 8.6.1 *Diet Instructions and Diet Records*) and supplementation with vitamin E and essential fatty acids (see Section 6.3 *Dietary Supplements*), is also specified, and dosing is escalated gradually to minimise GI side effects and allow for regular hepatic aminotransferase determination (see Section 7.2 *Treatment Schedule*). These elements of safety monitoring are designed to allow the optimum individualised dose to be selected for each patient in order to maximise the benefit of LDL-C reduction, ensure compliance with treatment, and avoid AEs.

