## 7.2 Treatment Schedule

After stabilisation of the patient on his/her current MTD of LLT (including LA when applicable) during the 6-week Run-in Period, treatment with lomitapide will be started as add-on therapy on D0 of the Efficacy Phase.

Lomitapide capsules will be provided in 4 dose strengths of 2 mg, 5 mg, 10 mg, and 20 mg. Dosing will be initiated at the recommended starting dose and escalated to the maximum dose as applicable to the age groups (see Table 2 and Figure 3) based upon safety and tolerability in addition to LDL-C values.

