#### **7.3.3 Dose Modification for Concomitant Medication**

##### **Weak Cytochrome P450 (CYP) 3A4 Inhibitors**

Medicinal products that induce CYP 3A4 would be expected to increase the rate and extent of metabolism of lomitapide. CYP 3A4 inducers exert their effect in a time-dependent manner, and may take at least 2 weeks to reach maximal effect after introduction. Conversely, on discontinuation, CYP 3A4 induction may take at least 2 weeks to decline.

Co-administration of a CYP 3A4 inducer is expected to reduce the effect of lomitapide. Any impact on efficacy is likely to be variable. When co-administering CYP 3A4 inducers (i.e., aminoglutethimide, naftacin, non-nucleoside reverse transcriptase inhibitors, phenobarbital, rifampicin, carbamazepine, pioglitazone, glucocorticoids, modafinil and phenytoin) with lomitapide, the possibility of a drug-drug interaction affecting efficacy should be considered.

Strong or moderate cytochrome CYP 3A4 inhibitors are not permitted during the study as described in Section 7.6.3 Non-Permitted Concomitant Medication, Food or Substances.

Weak cytochrome CYP 3A4 inhibitors are only permitted during the Safety Phase of the study, but lomitapide should be administered 12 hours apart. If atorvastatin is given concomitantly, it should be administered in the morning to separate it from lomitapide dosing by 12 hours. In case it is not possible to administer atorvastatin and lomitapide 12 hours apart, the lomitapide

dose should be reduced by half, as the lomitapide dose can be reduced from the MTD due to tolerability or safety issues during the 80-week Safety Phase. After a minimum period of 4 weeks following dose reduction the patient can be re-challenged with a higher dose of lomitapide once these issues resolve (i.e., if atorvastatin can be administered 12 hours apart or if atorvastatin is discontinued), but the dose during the Safety Phase cannot exceed the MTD established during the Efficacy Phase unless eligibility for exceptional dose escalation is met (described in Section 7.3.1 *Dose Escalation, Dose Reduction and Re-challenge*).

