### **HMG-CoA Reductase Inhibitors ('Statins')**

Lomitapide increases plasma concentrations of statins. Patients receiving lomitapide as adjunctive therapy to a statin should be monitored for AEs that are associated with the use of high doses of statins. Statins occasionally cause myopathy. In rare cases, myopathy may take the form of rhabdomyolysis with or without acute renal failure secondary to myoglobinuria, and can lead to fatality. All patients receiving lomitapide in addition to a statin should be advised of the potential increased risk of myopathy and told to report promptly any unexplained muscle pain, tenderness, or weakness (see Section 7.3.2 *Dose Modification, Interruption or Discontinuation for Adverse Events, Creatinine Kinase Monitoring and Evaluation*).

Concomitant administration of >40 mg simvastatin will not be permitted during the study as described in Section 7.6.3 Non-permitted Concomitant Medication, Food or Substances.

Since patients will be required to remain on their concomitant LLT (including LA, when applicable) established during the 6-week Run-in Period during the Efficacy Phase of the study through Week 24±3 days, a potential concomitant treatment with atorvastatin will remain unchanged during the Efficacy Phase, when lomitapide dosing will start. If atorvastatin is given concomitantly, it should be administered in the morning to separate it from lomitapide dosing by 12 hours. If during the 80-week Safety Phase it is not possible to administer atorvastatin and lomitapide 12 hours apart, the lomitapide dose should be reduced by half. After a minimum period of 4 weeks following dose reduction the patient can be re-challenged with a higher dose of lomitapide once these issues resolve (i.e., if atorvastatin can be administered 12 hours apart or if atorvastatin is discontinued), but the dose during the Safety Phase cannot exceed the MTD established during the Efficacy Phase unless eligibility for exceptional dose escalation is met (described in Section 7.3.1 *Dose Escalation, Dose Reduction and Re-challenge*).

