- Administration of non-permitted concomitant medication(s), substances, or foods
- Investigators’ decision that a change of therapy is in the patients’ best interest
- Occurrence of an AE (including abnormal laboratory findings), which makes discontinuation desirable or necessary in the investigators’ and/or the patients’ opinion

If a patient discontinues the study or the follow-up prematurely due to an AE/SAE, he/she will be followed up until the resolution or stabilisation of the AE/SAE.

If a patient discontinues the study prematurely, the EoT visit assessments should be made (see Section 9.7 *End of Treatment Visit*).

All data collected before premature discontinuation of the study will be used for analysis. Patients who drop out will not be replaced unless the assumptions for drop-out have been exceeded.

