### 7.6.2 Permitted Concomitant Medication

The following medication will be permitted during study and follow-up:

- Lipid-lowering medicinal products including statins, fibrates, bile acid sequestrants, and PCSK9 inhibitors

Please note: Patients who receive atorvastatin, should separate the dose of the medicinal products by 12 hours, e.g., by taking atorvastatin in the morning and lomitapide in the evening (see Section 7.3.3. *Dose Modification for Concomitant Medication*). Patients who receive bile acid sequestrants, should separate the dose of the medicinal products by 4 hours. Concomitant administration of >40 mg simvastatin is not permitted (see Section 7.6.3 *Non-permitted Concomitant Medication, Food or Substances*).

- Oestrogen-based oral contraceptives

Please note: Postmenarchal female adolescent patients taking oestrogen-based oral contraceptives should be advised that diarrhoea and/or vomiting may reduce hormone absorption. In case of protracted or severe diarrhoea and/or vomiting lasting more than 2 days, the investigator should advise according to national practice, which additional contraceptive measures (such as sexual abstinence, barrier methods) should be used for 7 days after resolution of symptoms.

- Supportive therapy upon the investigators' discretion.

The following medication will be permitted during the Safety Phase of the study:

- If a weak CYP 3A4 inhibitor, e.g., aminoglutethimide, naftillin, non-nucleoside reverse transcriptase inhibitors, phenobarbital, rifampicin, carbamazepine, pioglitazone, glucocorticoids, modafinil and phenytoin inhibitor is required during the Safety Phase, the dose of lomitapide should be reduced as described in Section 7.3.3 *Dose Modification for Concomitant Medication*.

Please note: Patients who receive weak CYP 3A4 inhibitors, should separate the dose of the medicinal products by 12 hours.

If atorvastatin is given concomitantly, it should be administered in the morning to separate it from lomitapide dosing by 12 hours. In case it is not possible to administer atorvastatin and lomitapide 12 hours apart, the lomitapide dose should be reduced by half (see Section 7.3.3 *Dose Modification for Concomitant Medication*).

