### **7.6.3 Non-permitted Concomitant Medication, Food or Substances**

#### **Non-permitted Concomitant Medication**

The following medication will not be permitted during the study:

- Contraindications for the use of lomitapide according to section 4.3 of the SPC (included in the Lojuxta® SPC in lieu of an IB; see Section 18.1 *Source Documents*), such as
  - Concomitant administration of >40 mg simvastatin.
  - Concomitant use of strong or moderate CYP 3A4 inhibitors, e.g., antifungal azoles such as itraconazole, fluconazole, ketoconazole, voriconazole, posaconazole; macrolide antibiotics such as erythromycin or clarithromycin; ketolide antibiotics such as telithromycin; HIV protease inhibitors; the calcium channel blockers diltiazem and verapamil, and the anti-arrhythmic dronedarone.

The following medication will not be permitted during the Efficacy Phase of the study:

- Weak CYP 3A4 inhibitors, e.g., aminoglutethimide, naftillin, non-nucleoside reverse transcriptase inhibitors, phenobarbital, rifampicin, carbamazepine, pioglitazone, glucocorticoids, modafinil and phenytoin. If a weak CYP 3A4 inhibitor is required during the Safety Phase, the dose of lomitapide should be reduced as described in Section 7.3.3 *Dose Modification for Concomitant Medication*.

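### Atorvastatin is both barred (as a weak CYP 3A4 inhibitor) and required to continue in the Efficacy Phase; the fallback for failed dose separation is tied to the Safety Phase and cannot be carried out at 2 mg or 5 mg

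*Protocol*

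**What the plan says.** **Class membership.** Section 2.6.3 reads "In the presence of atorvastatin (a weak CYP 3A4 inhibitor), lomitapide should be taken 12 hours apart". A few sentences later it turns to a different group with the words "For patients on a stable maintenance dose of lomitapide who receive any other weak CYP 3A4 inhibitor", so atorvastatin is treated as one member of the class.

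**The bar.** Section 7.3.3 says "Weak cytochrome CYP 3A4 inhibitors are only permitted during the Safety Phase of the study, but lomitapide should be administered 12 hours apart", and Section 2.6.2 says the same in substance. Section 7.6.3 lists weak CYP 3A4 inhibitors under the line "The following medication will not be permitted during the Efficacy Phase of the study", and the synopsis repeats this. None of these places exempts atorvastatin.

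**The requirement to continue.** The statin paragraph of Section 7.3.3 says that "a potential concomitant treatment with atorvastatin will remain unchanged during the Efficacy Phase, when lomitapide dosing will start". Section 7.6.1 forbids changes to background lipid-lowering therapy until Week 24. Section 7.6.2 and the synopsis list statins as permitted during the study and follow-up, with a note on the timing of atorvastatin.

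**The fallback.** Section 7.6.2, under its Safety Phase list, says: "In case it is not possible to administer atorvastatin and lomitapide 12 hours apart, the lomitapide dose should be reduced by half".

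**Supplied strengths.** Section 7.2: "Lomitapide capsules will be provided in 4 dose strengths of 2 mg, 5 mg, 10 mg, and 20 mg".

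**Consequences of a non-permitted drug.** Section 7.4 lists among the grounds on which the investigator may withdraw a patient: "Administration of non-permitted concomitant medication(s), substances, or foods". Section 13.2 has the monitor record use of prohibited medication as a deviation. Section 12.2 includes concomitant medication among the adherence checks for the per-protocol set.

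**The concern.** A site with a patient on atorvastatin is given two instructions that cannot both be followed before Week 24. If the patient stays on it, the patient is using a drug class barred in that phase. If the patient stops, background therapy has changed when it must not. The case is foreseeable: Section 7.6.1 describes a statin as the usual background treatment, and the published paediatric case summarised in Section 2.4.2 was on atorvastatin.

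Consistent conduct is at stake. Without a written rule, one monitor may log a deviation where another does not, and the data review meeting would then have to settle afterwards whether it counts.

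Two further gaps concern the same drug pair. The protocol says what to do if the two drugs cannot be taken 12 hours apart, but only in the Safety Phase. And the stated action, halving, has no executable form at the two lowest lomitapide doses.

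**Working it through.** **Step 1. Set the rules side by side for a patient whose stable background therapy includes atorvastatin.**

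| Question | Answer in the protocol | Where |
|---|---|---|
| Is atorvastatin a weak CYP 3A4 inhibitor? | Yes | 2.6.3 |
| Are weak CYP 3A4 inhibitors allowed in the Efficacy Phase? | No, no exception written | Synopsis, 2.6.2, 7.3.3, 7.6.3 |
| May atorvastatin be stopped or changed in the Efficacy Phase? | No | 2.6.3, 7.3.3, 7.6.1 |
| Are statins permitted throughout? | Yes, atorvastatin with 12-hour separation | Synopsis, 7.6.2 |

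Rows 1 and 2 together bar atorvastatin before Week 24. Rows 3 and 4 require or permit it in the same period.

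**Step 2. Can the list of examples settle it?** The drugs named as weak inhibitors in the synopsis and Section 7.6.3 do not include atorvastatin. The list is given only as examples, so absence from it does not exempt a drug. Section 7.3.3 also names the same drugs as CYP 3A4 inducers, so the list cannot show what the barred class contains.

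**Step 3. What applies if the 12-hour separation fails?**
- Separation itself: Section 7.2 states it without a phase limit, and Sections 7.3.3 and 7.6.2 carry it into the Efficacy Phase.
- Halving: Section 2.6.3 and the statin paragraph of Section 7.3.3 restrict it to the 80-week Safety Phase. The weak-inhibitor paragraph of Section 7.3.3 justifies it by what is allowed in that phase. The synopsis and Section 7.6.2 place it under a Safety Phase heading.
- Efficacy Phase: no specific instruction for failed separation is given.

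**Step 4. Can the halved dose be made?** Inputs: strengths 2, 5, 10 and 20 mg and 1 to 3 capsules a day (Section 7.2); doses 2, 5, 10, 20, 40 and 60 mg (Table 2). Assumption: whole capsules. The protocol allows a capsule to be opened and sprinkled but describes no part-capsule dosing.

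First, the protocol's own statement. All six Table 2 doses can be made with 1 to 3 capsules (for example 40 = 20 + 20 and 60 = 20 + 20 + 20), so it reproduces.

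Then half of each dose:

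| Dose (mg) | Half (mg) | From supplied capsules |
|---|---|---|
| 2 | 1 | cannot be made |
| 5 | 2.5 | cannot be made |
| 10 | 5 | one 5 mg |
| 20 | 10 | one 10 mg |
| 40 | 20 | one 20 mg |
| 60 | 30 | 20 mg + 10 mg |

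Allowing up to 10 capsules changes nothing in the first two rows: 1 mg is below the smallest capsule, and 2.5 mg is not a whole number of milligrams while every strength is. The general reduction rule in Section 7.3.1 (back to the last tolerated dose, or to one in between) does not supply either amount.

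**Step 5. How many patients?** The protocol gives no figure for atorvastatin use. Purely as an illustration, if 20% to 50% of about 45 enrolled patients took it, the contradictory rules would cover 0.20 × 45 = 9 to 0.50 × 45 = 22.5, that is 9 to 22 patients. The capsule problem needs a patient who is in the Safety Phase, on 2 mg or 5 mg, on atorvastatin and unable to separate the doses. The protocol gives no basis for counting that group.

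**The case against.** The best defence is that the specific text should override the general. Sections 2.6.3 and 7.3.3 deal with atorvastatin in the Efficacy Phase by name, Section 7.6.2 permits statins throughout, and Section 7.2 repeats the 12-hour separation. A sensible site would conclude that atorvastatin is allowed, and the sponsor probably meant an exemption. This stands as a reading of intent. It does not supply the missing exception, because a site or monitor applying Section 7.6.3 on its own finds a bar on the class to which Section 2.6.3 assigns atorvastatin.

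The other side is also right on reach. A reader might infer any of the following, and the documents do not support them:

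- **That the interaction is unregulated before Week 24.** Separation applies in that phase. It is also the default schedule, with atorvastatin in the morning and lomitapide after the evening meal. The general powers to reduce, hold or stop lomitapide in Sections 7.3.1 and 7.3.2 apply too. Only the specific fallback is missing.
- **That the primary endpoint is compromised.** The primary analysis uses the FAS, from which this conflict removes nobody, and Section 12.3 names a treatment-policy estimand. No figure in the protocol shows an effect on the maximum tolerated dose or on LDL-C. Section 2.6.2 says that lomitapide's activity does not depend on systemic exposure.
- **That halving is impossible during the early titration weeks.** Those weeks lie in the Efficacy Phase, where the halving rule as written does not operate.
- **That patients on atorvastatin will be withdrawn or dropped from the per-protocol set.** Withdrawal on this ground is at the investigator's discretion. Per-protocol exclusion is decided case by case for important deviations, and that set is supplementary.

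**Conclusion.** The point holds as an inconsistency in the protocol's rules, in three parts.

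1. A patient on atorvastatin cannot literally comply with both the bar on weak CYP 3A4 inhibitors and the requirement to keep background therapy unchanged in the Efficacy Phase. The patient may therefore be recorded as using a non-permitted drug.
2. The fallback for failed separation is tied to the Safety Phase, so the Efficacy Phase has no specific instruction.
3. In the Safety Phase, the fallback cannot be carried out at two of the six Table 2 dose levels, 2 mg and 5 mg. This assumes whole-capsule dosing.

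The size in patients is not known. The range of 9 to 22 patients for the first part rests wholly on an assumed rate of atorvastatin use, and the third part may concern few patients or none. The effect falls on consistent site conduct, deviation recording and the per-protocol review, and on whether a stated safety rule can be followed. It does not reach the primary analysis set. The point should be corrected because two rules cannot be followed as written and the remedy is cheap.

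**What to change.** Reconcile Sections 2.6.2, 2.6.3, 7.3.3 and 7.6.1 to 7.6.3 with each other and with the synopsis:

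- State in Sections 7.3.3 and 7.6.3 whether atorvastatin falls under the Efficacy Phase bar. If it does not, name it as an exception and say that its use is neither a protocol deviation nor a ground for withdrawal.
- State in which phases the rule for failed 12-hour separation applies.
- Word that rule so that it can be carried out with the supplied strengths at every dose to which it applies.

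The sponsor's clinical team decides the content; no dose or clinical rule is proposed here. The cost is a protocol wording change and matching site guidance. No change to data collection, sample size or the primary analysis is needed.

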### **HMG-CoA Reductase Inhibitors ('Statins')**

Lomitapide increases plasma concentrations of statins. Patients receiving lomitapide as adjunctive therapy to a statin should be monitored for AEs that are associated with the use of high doses of statins. Statins occasionally cause myopathy. In rare cases, myopathy may take the form of rhabdomyolysis with or without acute renal failure secondary to myoglobinuria, and can lead to fatality. All patients receiving lomitapide in addition to a statin should be advised of the potential increased risk of myopathy and told to report promptly any unexplained muscle pain, tenderness, or weakness (see Section 7.3.2 *Dose Modification, Interruption or Discontinuation for Adverse Events, Creatinine Kinase Monitoring and Evaluation*).

Concomitant administration of >40 mg simvastatin will not be permitted during the study as described in Section 7.6.3 Non-permitted Concomitant Medication, Food or Substances.

Since patients will be required to remain on their concomitant LLT (including LA, when applicable) established during the 6-week Run-in Period during the Efficacy Phase of the study through Week 24±3 days, a potential concomitant treatment with atorvastatin will remain unchanged during the Efficacy Phase, when lomitapide dosing will start. If atorvastatin is given concomitantly, it should be administered in the morning to separate it from lomitapide dosing by 12 hours. If during the 80-week Safety Phase it is not possible to administer atorvastatin and lomitapide 12 hours apart, the lomitapide dose should be reduced by half. After a minimum period of 4 weeks following dose reduction the patient can be re-challenged with a higher dose of lomitapide once these issues resolve (i.e., if atorvastatin can be administered 12 hours apart or if atorvastatin is discontinued), but the dose during the Safety Phase cannot exceed the MTD established during the Efficacy Phase unless eligibility for exceptional dose escalation is met (described in Section 7.3.1 *Dose Escalation, Dose Reduction and Re-challenge*).

